## 8.6. Examination of Subgroups

No subgroup analyses are planned.

# 9. SAFETY EVALUATION

## 9.1. Overview of Safety Analysis Methods

All safety summaries will be descriptive with no statistical hypothesis testing and based on the Safety Population. Patients will be summarized according to the study drug received (ie, as treated), should it differ from the randomized treatment arm. Safety assessments will be summarized by treatment group and overall. All safety endpoints will be listed in by-patient data listings.

#### 9.2. Extent of Exposure

Study drug exposure will be summarized for each treatment group. The number of days on which study drug was dosed (at least partially), the number of days in the study, percent of planned doses received, and total cumulative dose will be summarized for each treatment group.

The number of days on which study drug was dosed (at least partially) will be calculated as (treatment end date – treatment start date + 1) minus the total number of days with a dosing exception per the *Dosing Exceptions* eCRF page of partial dose (counted as 1 day missed), missed dose (counted as 1 day missed), or dose interruption (counted as 1 day missed). The number of days in the study will be calculated as (treatment end date – treatment start date + 1). Total cumulative dose will be calculated as the total number of tablets taken multiplied by 8 mg, 12 mg, or 0 mg for each applicable treatment.

The number and percentage of subjects with at least one dose interruption will also be summarized, where dose interruption is defined as a value of "Dose interruption" for the question "Reason for Exception" on the *Dosing Exceptions* eCRF page. The sponsor may review the free text field associated with the "Reason for Exception" prior to database lock in order to identify reasons related to the dose interruption criteria outlined in Protocol Section 9.2.1. Should these reasons be identified, the definition of dose interruption would be refined based on those findings.

Drug compliance will also be summarized, per Section 7.3.

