## **Duration of study participation:**

Upon completion of the 24-week Treatment Period, patients will be eligible to either enroll in the Open-Label Extension study or complete treatment and exit the study following the 4-week Safety Follow-up visit. Patients will participate in the study for up to 32 weeks if they decide not to enroll in the Open-Label Extension study (4-week Screening, 24-week Treatment, 4-week Safety Follow-up). Otherwise study duration will be up to approximately 28 weeks.

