## 8.3. Patient Withdrawal Criteria

For all patients, it is the intent that patients who discontinue study medication (at any time) for any reason will continue to be followed for all protocol-planned study visits through the completion of the 24-week treatment period, and will have all endpoints (including efficacy) collected accordingly.

The Investigator, Sponsor, or its designee may decide a patient should discontinue treatment at any time and for any reason. In addition, patients will discontinue randomized treatment if they:

- Experience an intolerable adverse event: such events include, but are not limited to, adverse events ≥ Grade 4\*, bone marrow-related events, a ≥ Grade 3\* cardiac event (\*CTCAE v5.0 criteria);
- Require a medication that is prohibited by the protocol. However, under certain circumstances, and in consultation with the Medical Monitor, short-term use of a prohibited medication may not necessitate withdrawal of treatment when its use is unlikely to unfavorably alter the risk-benefit of subject participation;
- In the opinion of the Investigator, have any medically appropriate reason;
- Become pregnant;
- Have a serious adverse event associated with a SARS-CoV-2 infection;
- The Investigator believes that further treatment is undesirable or the risk-benefit profile has become unfavorable.

Furthermore, dose interruptions lasting more than 21 days may require treatment discontinuation on a case by case basis following consultation with the Medical Monitor.

In addition, patients are free to withdraw from participation in the study at any time, for any reason, and without prejudice. The Investigator must withdraw any patient from the study if the patient withdraws consent and requests to stop participating in the study. Patients who withdraw or are withdrawn from the study will not be replaced.

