# 7.3. Measures of Treatment Compliance

Patients will strive for 100% compliance with the daily dosing schedule. Treatment compliance will be summarized as percent of planned dose received for each dosing regimen. Percent of planned dose received will be calculated for the entire treatment period as follows:

100\*(Tablets Dispensed-Tablets Returned)/(Tablets Expected)

Tablets Expected is defined as the time on treatment multiplied by the expected number of pills taken daily (x2 for the 12 mg BID group; x2 for the 8 mg BID group; x2 for the placebo group), where time on treatment is defined as treatment end date – treatment start date + 1. Dose

interruptions will be ignored in this calculation. Derived patient compliance, compliance per the eCRF (80% or higher versus less than 80%), and dosing exceptions will be listed in by-patient data listings.

For patients who roll over into one of the open label extension studies, it will be assumed that only 1 dose of study drug was administered for the last dose of study drug. For patients who do not roll over, it will be assumed that 2 doses of study drug were administered for the last dose of study drug.

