#### 8.1.2. **Assessment Time Windows**

The visit schedule for all study assessments is provided in Appendix 15.2. Patients will be considered completed for efficacy analyses after Week 24 (Visit 9). Patients will either complete treatment at Week 24 and have a safety follow-up visit at Week 28 (Visit 10) prior to exiting the study, or if eligible, may enroll into an open-label extension study of CTP-543 at their Week 24 visit.

Unscheduled visits and early termination visits will be reassigned based on the analysis windows in the below table and the schedule of events. Assessments may only be re-assigned to visits where they were to be collected per the schedule of events. The latest assessment in a window will be selected as the visit used in summaries, unless otherwise specified. All visits will be included in by-patient data listings.

	Safety Analyses				Efficacy Analyses			
Nominal Visit	Lower	Lower Target Upper		Lower	Target	Upper		
Screening	-28	-1	-1	-28	-1	-1		
Visit 2-Day 1	1	1	1	1	1	1		
Visit 3-Week 2	2	15	22	12	15	18		
Visit 4-Week 4	23	29	43	26	29	32		
Visit 5-Week 8	44	57	71	54	57	60		
Visit 6-Week 12	72	85	99	82	85	88		
Visit 7-Week 16	100	113	127	110	113	116		
Visit 8-Week 20	128	141	155	138	141	144		
Visit 9-Week 24	156	169	183	166	169	172		
Visit 10-Week 28	184	197	211	194	197	200		

Table 2: Analysis Windows for Unscheduled and Early Termination Visits

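### SAP 9.2 counts days dosed at least partially but subtracts every partial-dose day; its days-in-study measure is in fact treatment duration

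*SAP*

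**What the plan says.** SAP 9.2 names four exposure measures: days dosed, days in the study, percent of planned doses received, and total cumulative dose.

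The first is introduced with "The number of days on which study drug was dosed (at least partially) will be calculated as" the treatment span (end date minus start date plus 1) minus the days that the Dosing Exceptions eCRF page records as "partial dose (counted as 1 day missed), missed dose (counted as 1 day missed), or dose interruption (counted as 1 day missed"). Each of the three exception types therefore removes one whole day.

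The second is introduced with "The number of days in the study will be calculated as" that same treatment span, with nothing subtracted. SAP 7.3 uses the identical expression under another name: "where time on treatment is defined as treatment end date" minus treatment start date plus 1.

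The fourth is a tablet count: "Total cumulative dose will be calculated as the total number of tablets taken multiplied by" the tablet strength.

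Protocol 12.4.7 is shorter. It plans a summary of the days on which drug was dosed, and the only exclusion it names for total days on drug is dose interruptions. SAP Section 13, which lists departures from the protocol, has no entry for Protocol 12.4.7.

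**The concern.** The name of the first measure and its formula disagree about partial-dose days. Dosing is one tablet in the morning and one in the evening (Protocol 9.4.3), so a half-dosed day is an ordinary event, and the SAP text treats partial dose as its own exception type. SAP Section 2 gives the SAP precedence over the protocol, so the formula would be programmed as written. The result would be a count of days without a recorded exception, reported as a count of days with any drug.

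The second measure has a milder version of the same fault. Protocol 8.3 says patients who stop drug "will continue to be followed for all protocol-planned study visits through the completion of the 24-week treatment period". SAP 8.1.2 says patients who do not enter the extension "complete treatment at Week 24 and have a safety follow-up visit at Week 28 (Visit 10) prior to exiting the study". The protocol synopsis likewise provides that "Patients will participate in the study for up to 32 weeks if they decide not to enroll in the Open-Label Extension study". For both groups study time runs past the last dose, and a span ending on the treatment end date cannot show it.

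At stake is the accuracy of two of the four exposure measures. If partial-dose days are more frequent in one arm, the understatement also differs between arms.

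**Working it through.** SAP 9.2 states no figure, so there is none to reproduce. The check compares each formula with the name it carries.

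**Days dosed**

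Notation:
- S = treatment end − treatment start + 1
- k = partial-dose days
- m = days with no dose taken
- i = interruption days

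Formulas:
- SAP 9.2 formula: S − k − m − i
- Meaning of the name (any drug taken that day): S − m − i
- Difference: (S − m − i) − (S − k − m − i) = k

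Inputs: S = 24 × 7 = 168 days, with m = i = 0. The values of k are assumed, because neither document gives a rate of partial dosing.

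| k (assumed) | SAP formula | Days with any drug | Formula as % of days with any drug | Shortfall |
|---|---|---|---|---|
| 0 | 168 | 168 | 100% | 0 |
| 1 | 167 | 168 | 99.4% | 0.6% |
| 5 | 163 | 168 | 97.0% | 3.0% |
| 10 | 158 | 168 | 94.0% | 6.0% |
| 20 | 148 | 168 | 88.1% | 11.9% |

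Other exceptions do not change the gap. With k = 10, m = 2 and i = 7, the formula gives 168 − 19 = 149 and the name means 168 − 9 = 159, again 10 apart.

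This takes m to be days on which nothing was taken. The documents do not define the eCRF category for a missed dose. If it can be one of the two daily tablets, some of those days were also partly dosed, and the shortfall is larger than k.

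**Days in the study**

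Inputs are the target days in SAP Table 2: Week 8 = Day 57, Week 12 = Day 85, Week 24 = Day 169, Week 28 = Day 197. Both spans are counted from Day 1.

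| Assumed patient | SAP formula | Day 1 to last study visit | Short by |
|---|---|---|---|
| Treatment ends Day 57, followed to Week 24 | 57 − 1 + 1 = 57 | 169 | 112 days (57/169 = 33.7%) |
| Treatment ends Day 85, followed to Week 24 | 85 − 1 + 1 = 85 | 169 | 84 days (85/169 = 50.3%) |
| Completer, treatment ends Day 169, no rollover, Week 28 visit | 169 − 1 + 1 = 169 | 197 | 28 days (169/197 = 85.8%) |

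Because the expression is the one SAP 7.3 calls time on treatment, the two quantities are equal for every patient.

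**The case against.** The best reply is that this is a naming fault and not a calculation error. The rule is explicit, two programmers would obtain the same number, and the mock tables that carry the printed labels and footnotes are not in the published text. That is fair as a description: changing the name alone would cure it. It does not remove the conflict, because the SAP text itself gives the measure one meaning and a formula with another. If subtracting partial days was a deliberate cautious convention, the name is what has to change.

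A second reply is that little depends on it. This largely stands. SAP 9.1 makes all safety summaries descriptive. Cumulative dose and compliance rest on tablet counts, dose interruptions are also summarized separately, and the adverse event intervals use numbers of patients as denominators. The subtraction can only understate days of exposure. These points limit the consequence but do not correct the mislabelled count.

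Third, the size of the days-in-study gap depends on where the study is taken to begin. The protocol's 32 weeks (32 × 7 = 224 days) include screening, whereas the figures above start at Day 1. The choice of start is open, but any start at or before Day 1 leaves the same days missing after the last dose.

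**Conclusion.** The concern holds. As written, the SAP 9.2 count of days dosed is short by one day per partial-dose day relative to its own name. Protocol 12.4.7 does not call for that subtraction, and SAP Section 13 does not declare it as a change.

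On an assumed 1 to 20 partial days in 168, the shortfall is 0.6% to 11.9%. With no partial days it is zero, and it exceeds one day per partial-dose day if missed-dose entries include half-dosed days. The days-in-study measure is treatment duration under another name, short by 28 to 112 days in the three illustrative patients.

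The effect stops at these two descriptive measures. Efficacy results, type I error, power, cumulative dose and compliance are unchanged.

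**What to change.** For days dosed, stop subtracting partial-dose days and subtract only days on which no tablet was taken. If the Dosing Exceptions page cannot identify those days, keep the formula, remove the parenthetical about partial dosing, and name the measure days without a recorded dosing exception. Either way, state in SAP 9.2 how a missed-dose entry is counted when only one of the two tablets was missed.

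For days in the study, rename the measure treatment duration (days). Alternatively, calculate it from study dates with the start day stated, using the end-of-study date that SAP 6.1 already lists for each patient.

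The cost is one derivation line or one label for the first measure and one label for the second. The relabelling route needs no new data. The derivation route depends on whether the eCRF separates days with no tablet from half-dosed days.

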#### 9.3. Adverse Events

An adverse event is any untoward medical occurrence that may appear or worsen in a patient during the course of a study. It may be a new intercurrent illness, a worsening concomitant illness, an injury, or any concomitant impairment of the patient's health, including laboratory test values, regardless of etiology. Any worsening (ie, any clinically significant adverse change in the frequency or intensity of a pre-existing condition) should be considered an adverse event. A diagnosis or syndrome should be recorded on the adverse event page of the eCRF rather than the individual signs or symptoms of the diagnosis or syndrome. A worsening of the condition under study, alopecia areata, will not be reported as an adverse event.

All patients will be monitored for adverse events during the study. Assessments may include monitoring of the following parameters: the patient's clinical symptoms, laboratory, physical examination findings, or findings from other tests and/or procedures.

Adverse events will be coded using MedDRA version 23.1 and summarized by treatment group, system organ class, and preferred term.

An adverse event reported after informed consent, but before the first dose of study drug (i.e., Day 1), will be considered a pre-treatment adverse event. Treatment-emergent adverse events will be defined as any adverse event that occurs after administration of the first dose of study drug. Adverse events will be limited to those collected within this protocol (ie, for rollover subjects, AEs collected under the protocol of the rollover study will not be in this study). The number and percentage of patients who report TEAEs will be summarized by treatment group, system organ class, and preferred term.

Treatment emergent adverse events will also be summarized by intensity as well as relationship to study drug.

Partial dates will be imputed for the purposes of defining TEAEs as follows:

- For a missing start day where the month and year are present, the start day will be set to the first day of the month, unless 1) the first day of the month is before the date of administration of study drug and the month and year are the same as the month and year of the date of administration of study drug, and 2) the end date is on or after the date of administration of study drug or the end date is completely missing, in which case the start day will be set to the first day of administration of study drug.
- For a missing start day and month where the year is present, the start day and month will be set to January 1st, unless 1) January 1st is before the date of administration of study drug, and 2) the end date is on or after the date of administration of study drug or the end date is completely missing, in which case the start day and month will be set to that of the first date of administration of study drug.
- For an entirely missing start date (ie day, month, and year are missing), the start date will be set to the date of administration of study drug unless the stop date is prior to the date of administration of study drug, in which case the start date will be set to the stop date.
- For a missing end day where the month and year are present, the end day will be set to the last day of the month, unless the month and year are the same as the month and year of the last visit date for the patient, in which case the end day will be set to that of the patient's last visit date.
- For a missing end day and month where the year is present, the end day and month will be set to the patient's last visit date, unless the year of the patient's last visit date is greater than the end year, in which case the end day and month will be set to December 31st.
- For an entirely missing stop date (i.e. day, month, and year are missing), the stop date will be imputed as the patient's last visit date.

Patients who report the same preferred term on multiple occasions will be counted once for the preferred term: under the highest severity when summarized by severity and under the closest relationship to study drug when summarized by relationship. Missing severity or relationship will not be imputed. If a patient reports multiple preferred terms for a system organ class, the patient will be counted only once for that system organ class.

The number and percentage of patients who experience TEAEs and the total number of TEAEs will be summarized by treatment group and overall for the following:

- By system organ class and preferred term
- By severity/intensity, system organ class, and preferred term
- By relationship to study drug, system organ class, and preferred term
- Serious adverse events by system organ class and preferred term
- Serious adverse events by relationship to study drug, system organ class, and preferred term
- Adverse events resulting in discontinuation of study drug by system organ class and preferred term
- Adverse events that result in study drug dose interruption by system organ class and preferred term

Additionally, TEAEs will be summarized by treatment group and overall and by time interval: 0 to 12 weeks, and 12 to 24 weeks. For each time interval, an incidence table will summarize only TEAEs with an onset date within the interval and a prevalence table will summarize all TEAEs that have an onset date within the interval or continue into the interval. Differences between the incidence and prevalence tables can provide insight into the duration of TEAEs as well as the recurrence of TEAEs. A preferred term for an individual patient will be reported in multiple time intervals if there are multiple adverse event reports. The denominator for each time interval will be the number of patients who received at least 1 dose of study drug within the interval.

By-patient listings will include all adverse events. TEAEs will be flagged.

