## 11.5. Recording Adverse Events

All adverse events (regardless of seriousness or relationship to study drug) including those from the time informed consent is obtained through to the final study visit are to be recorded in the eCRF. Each individual adverse event is to be listed as a separate entry. The Investigator will provide information about dates of onset and resolution, seriousness, severity, action(s) taken, outcome, and relationship to the study drug. All adverse events should be documented in the patient's source documents.

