#### **Adverse Events**

An adverse event reported after informed consent, but before the first dose of study drug (i.e., Day 1), will be considered a pre-treatment adverse event. Treatment-emergent adverse events (TEAEs) will be defined as any adverse event that occurs after administration of the first dose of study drug through to the final study visit. The number and percentage of patients who report TEAEs will be summarized by system organ class and preferred term.

Treatment emergent adverse events will also be summarized by intensity as well as relationship to study drug.

Patients who report the same preferred term on multiple occasions will be counted once for the preferred term: under the highest severity when summarized by severity and under the closest relationship to study drug when summarized by relationship. If a patient reports multiple preferred terms for a system organ class, the patient will be counted only once for that system organ class.

Proportions for adverse events that are gender-specific (e.g., dysmenorrhea) will be based on the number of patients from that gender.

The number and percentage of patients who experience TEAEs will be summarized by treatment group for the following:

- By system organ class and preferred term
- By severity/intensity, system organ class, and preferred term
- By relationship to study drug, system organ class, and preferred term
- Serious adverse events by system organ class and preferred term
- Serious adverse events by relationship to study drug, system organ class, and preferred term
- Adverse events resulting in discontinuation of study drug by system organ class and preferred term
- Adverse events that result in study drug dose interruption by system organ class and preferred term

By-patient listings will be provided for any deaths, serious adverse events, and adverse events leading to discontinuation of treatment. Treatment-emergent adverse events that result in dose interruption will also be identified.

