#### 5. ANALYSIS SAMPLES

The Efficacy Population will include all patients who are randomized in the study and dispensed study drug during the Treatment Period and were not treated at site 102. It was determined by the Sponsor during the course of the study that site 102 would be early terminated due to continued failure to comply with study procedures. The decision to exclude subjects treated at site 102 was made prior to unblinding.

The Modified Efficacy Population will include all patients who are randomized in the study and dispensed study drug during the Treatment Period. This population will include subjects from site 102 and will be used for sensitivity analyses of the primary and key secondary endpoints.

The Pharmacokinetic Population will include all patients who receive study drug and have at least 1 pharmacokinetic sample taken during the Treatment Period. Patients who receive placebo will be excluded from the Pharmacokinetic Population.

The Safety Population will include all patients who receive study drug during the Treatment Period. The Safety Population will include patients from site 102.

The Per Protocol Population will include all patients in the Efficacy Population who were dosed according to protocol and have no major protocol deviations. Further details on the identification of major protocol deviations are provided in Section 7.1.

In the event patients incorrectly receive treatment associated with a different treatment group, they will be analyzed "as randomized" for efficacy and "as treated" for safety if the patient received that treatment for more than 50% of doses.

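### Week 12–24 adverse event percentages can count patients in the numerator whom the denominator leaves out

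*SAP*

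**What the plan says.** - **Denominator.** SAP 9.3: "The denominator for each time interval will be the number of patients who received at least 1 dose of study drug within the interval". Protocol 12.4.8 gives the same rule.
- **Numerator, incidence.** SAP 9.3: "an incidence table will summarize only TEAEs with an onset date within the interval".
- **Numerator, prevalence.** SAP 9.3: "a prevalence table will summarize all TEAEs that have an onset date within the interval or continue into the interval".
- **What counts as a TEAE.** SAP 9.3: "Treatment-emergent adverse events will be defined as any adverse event that occurs after administration of the first dose of study drug". Protocol 12.4.8 closes the window at the last visit, not the last dose: "any adverse event that occurs after administration of the first dose of study drug through to the final study visit".
- **Follow-up after stopping drug.** Protocol 8.3 says that patients who stop study drug "will continue to be followed for all protocol-planned study visits through the completion of the 24-week treatment period".
- **Recording.** Protocol 11.5 covers all adverse events, "including those from the time informed consent is obtained through to the final study visit are to be recorded in the eCRF".
- **Who is in the safety set.** SAP Section 5: "The Safety Population will include all patients who receive study drug during the Treatment Period". Early stoppers therefore belong to it.

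**The concern.** A percentage of patients with an event needs a numerator drawn from its denominator. Here the denominator is limited by dosing and the numerator is not. Take a patient who stops drug at Week 8, stays in follow-up and has a new event at Week 16. That event is a TEAE with onset in Weeks 12–24, so the patient enters the incidence numerator. The patient took no drug in that interval, so the denominator omits them.

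The prevalence table is the more exposed of the two. An event that led to stopping before Week 12 and is still ongoing is carried into the second interval, while the patient who has it is left out below the line. SAP 9.3 also sets a wholly missing stop date to the patient's last visit, which keeps such an event open for as long as the patient is followed.

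These tables are meant to show how adverse events change over time. An upward error confined to the later interval would blur that picture. If stopping differs between arms, it would also affect the comparison of arms within Weeks 12–24.

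**Working it through.** The documents state no interval percentage, so there is no figure to reproduce. The check is on the rule itself.

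**Inputs from the documents.** The definitions quoted above, and the planned arm sizes of 110, 220 and 110 (protocol 12.1).

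**Inputs assumed.** 5–20% of an arm stop drug before Week 12 and all remain in follow-up; 20% of dosed patients have a TEAE in Weeks 12–24. The documents give none of these.

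**Step 1: which interval is affected.** Every Safety Population patient takes the first dose on Day 1, so all are in the Weeks 0–12 denominator. A mismatch can arise only in Weeks 12–24.

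**Step 2: formulas.** Among patients still followed, let n_on be those dosed in Weeks 12–24 and n_off those who stopped earlier. Let x_on and x_off be the patients in each group with a counted TEAE.

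- Rule as written: R = (x_on + x_off) / n_on
- Consistent rate A, dosed patients only: x_on / n_on
- Consistent rate B, all followed patients: (x_on + x_off) / (n_on + n_off)

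R is never below A or B, and it exceeds both once n_off and x_off are above zero. The ratios are R/B = (n_on + n_off) / n_on, whatever the event rates, and R/A = 1 + x_off / x_on.

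**Step 3: R/B at assumed stopping fractions** (whole patients)

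| Off drug by Week 12 | Arm of 110: off / dosed | R/B | Arm of 220: off / dosed | R/B |
|---|---|---|---|---|
| 5% | 6 / 104 | 1.058 | 11 / 209 | 1.053 |
| 10% | 11 / 99 | 1.111 | 22 / 198 | 1.111 |
| 15% | 16 / 94 | 1.170 | 33 / 187 | 1.176 |
| 20% | 22 / 88 | 1.250 | 44 / 176 | 1.250 |

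**Step 4: dependence on the off-drug event rate.** Arm of 110 with 11 off drug, so x_on = 0.20 × 99 = 19.8.

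- Off-drug rate 0%: R = 19.8/99 = 20.0%, equal to A. B = 19.8/110 = 18.0%.
- Off-drug rate 20%: x_off = 2.2; R = 22.0/99 = 22.2%; A = 20.0%; B = 22.0/110 = 20.0%.
- Off-drug rate 40%: x_off = 4.4; R = 24.2/99 = 24.4%; A = 20.0%; B = 24.2/110 = 22.0%.

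**Step 5: a single preferred term in the prevalence table.** Same arm, with 5 dosed patients and 3 stoppers having the event: R = 8/99 = 8.08%, against A = 5/99 = 5.05% and B = 8/110 = 7.27%.

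**Step 6: two arms.** Suppose the event rate is 20% in both arms, on and off drug, with 15% off drug in one arm and 5% in the other. The table would show 20/0.85 = 23.5% and 20/0.95 = 21.1%, a gap of about 2.5 points where none exists.

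**Step 7: interval limits.** The two intervals share Week 12, which is Day 85 in SAP Table 2. An onset on that day belongs to both.

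**The case against.** The best defence is that SAP 9.3 never says that undosed patients are counted. On this view the patients dosed in the interval are the set being summarised, and the numerator is implicitly theirs. SAP Section 4 leans that way: its default denominator is the population being summarised, and it keeps data from patients excluded from an analysis population out of summary statistics. The mock tables attached to the SAP might also settle the matter, but they are not available here.

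This does not repair the text. The Section 4 rules concern analysis populations, and the interval set is not among those named in SAP Section 5. SAP 9.5 shows that the authors restrict to on-treatment data explicitly when they mean to, as they do for several laboratory summaries. SAP Section 13 revises another adverse event denominator (sex-specific events) and leaves this one alone.

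Several limits on the point do stand:

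- A reader might infer that the late-interval rates will be inflated as a matter of course, by a known amount. The documents do not support that. An excess over the dosed-patient rate needs at least one early stopper, still followed, with a counted event in Weeks 12–24. Patients who leave the study contribute no events after exit.
- A reader might infer a bias for or against a particular arm. Nothing in the documents shows which arm would stop more.
- A reader might infer that events in Weeks 24–28 are lost. That follow-up applies only to patients who do not roll over, it comes after treatment ends, and its events remain in the overall tables and the listings.
- Safety summaries carry no hypothesis tests. The planned Kaplan-Meier curve of time to early treatment termination would show any difference in stopping between arms.

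**Conclusion.** The point holds as a defect in a stated rule, of minor consequence. Followed literally, SAP 9.3 and protocol 12.4.8 allow a patient to be counted in the Week 12–24 numerator and not in its denominator. The direction is certain: the percentage is too high whenever such a patient has a counted event, and otherwise it equals the rate among dosed patients. Weeks 0–12 and the overall Safety Population TEAE tables are unaffected.

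The size cannot be computed from the documents. Relative to the rate in all followed patients, the factor is the number followed divided by the number dosed: about 1.05–1.25 if 5–20% are off drug by Week 12 and all remain followed. The excess over the dosed-patient rate depends further on the off-drug event rate, which is also unknown. The illustrations above rest on these assumptions and are not forecasts.

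**What to change.** Make numerator and denominator the same set of patients, in one of two ways:

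- **(a)** Use as denominator the Safety Population patients still under adverse event observation at the start of the interval. This keeps all recorded events and describes everyone followed.
- **(b)** Keep the prespecified denominator and count only TEAEs in patients dosed in the interval, with a stated on-treatment window. This stays closest to the protocol and describes patients on drug.

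Either removes the mismatch; the choice depends on which question the table should answer. Apply it to both the incidence and the prevalence tables.

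Also assign the Week 12 boundary day to one interval, using the SAP Table 2 calendar (Week 12 = Day 85, Week 24 = Day 169). Ending the second interval at Day 168 (24 × 7) would not fit that calendar, because it would put onsets on the nominal Week 24 visit day outside the interval.

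The cost is a few sentences in SAP 9.3, an entry in SAP Section 13 because the protocol has the same rule, and a small amount of programming. No new data are needed. The downside is a departure from the protocol wording.
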